5.4.2.1. Management of New or Worsening Pulmonary Symptoms

If new or worsening pulmonary symptoms (e.g. dyspnoea) or radiological abnormalities occur in the absence of a clear diagnosis, an interruption in study treatment dosing is recommended and further diagnostic workup (including a high resolution CT scan) should be performed, to exclude pneumonitis.

Following investigation, if no evidence of abnormality is observed on CT imaging and symptoms resolve, then olaparib treatment can be restarted, if deemed appropriate by the Investigator. If significant pulmonary abnormalities are identified, these need to be discussed with GEICAM.

5.4.2.2. Management of Nausea and Vomiting

Events of nausea and vomiting are known to be associated with olaparib treatment. In study D0810C00019 nausea was reported in 71% of the olaparib treated patients and 36% in the placebo treated patients and vomiting was reported in 34% of the olaparib treated patients and 14% in the placebo treated patients. These events are generally mild to moderate (NCI-CTCAE grade 1 or 2) severity, intermittent and manageable on continued treatment. The first onset generally occurs in the first month of treatment for nausea and within the first 6 months of treatment for vomiting. For nausea, the incidence generally plateaus at around 9 months, and for vomiting at around 6 to 7 months.

No routine prophylactic anti-emetic treatment is required at the start of study treatment; however, patients should receive appropriate anti-emetic treatment at the first onset of nausea or vomiting and as required thereafter, in accordance with local treatment practice guidelines. Alternatively, olaparib tablets can be taken with a light meal/snack (e.g. 2 pieces of toast or a couple of biscuits).

As per international guidance on anti-emetic use in cancer patients (ESMO, NCCN), generally a single agent antiemetic should be considered e.g. dopamine receptor antagonist, antihistamines or dexamethasone.

5.4.2.3. Management of Renal Impairment

If subsequent to study entry and while still on study therapy, a patient's estimated CrCl falls below the threshold for study inclusion (≥ 51 ml/min), retesting should be performed promptly.

A dose reduction is recommended for patients who develop moderate renal impairment (calculated creatinine clearance by Cockcroft-Gault equation of between 31 and 50 ml/min) for any reason during the course of the study: the dose of olaparib should be reduced to 200 mg b.i.d.

Because the CrCl determination is only an estimate of renal function, in instances where the CrCl falls to between 31 and 50 mL/min, the investigator should use his or her discretion in determining whether a dose change or discontinuation of therapy is warranted.

Olaparib has not been studied in patients with severe renal impairment (creatinine clearance \leq 30 ml/min) or end-stage renal disease; if patients develop severe impairment or end stage disease is it recommended that olaparib be discontinued.

5.4.3. Interruptions for Intercurrent Non-toxicity Related Events

Study treatment dose interruption for conditions other than toxicity resolution should be kept as short as possible. If a patient cannot restart study treatment within 4 weeks for resolution of intercurrent conditions not related to disease progression or toxicity, the case should be discussed with GEICAM.

All dose reductions and interruptions (including any missed doses), and the reasons for the reductions/interruptions are to be recorded in the eCRF.

Study treatment should be stopped at least 3 days prior to planned surgery. After surgery study treatment can be restarted when the wound has healed. No stoppage of study treatment is required for any needle biopsy procedure.

Study treatment should be discontinued for a minimum of 3 days before a patient undergoes radiation treatment. Study treatment should be restarted within 4 weeks as long as any bone marrow toxicity has recovered.

Because the AEs related to olaparib may include asthenia, fatigue and dizziness, patients should be advised to use caution while driving or using machinery if these symptoms occur.

Table 9. Dose reductions for study treatment

Initial Dose	Following re-challenge post interruption: Dose reduction 1	Dose reduction 2
300 mg twice daily	250 mg twice daily	200 mg twice daily

5.4.4. Medication Errors and Overdose

Medication errors may result in the administration or consumption of the wrong drug, by the wrong patient, at the wrong time or at the wrong dosage strength. If patient taking the lower dosing consciously/deliberately and not by mistake (e.g. if the patient is not

tolerating the full dose very well), then this isn't a medication error. Such medication errors occurring to a study participant are to be captured on the adverse event (AE) page of the eCRFs and on the SAE form when appropriate. In the event of medication dosing error GEICAM should be notified immediately. If an overdose or lower dose on olaparib occurs in the course of the study and it is associated with an AE (serious or not) are to be reported within 24 hours on a SAE form. Overdoses which are not associated with any AE can be reported within 30 days in a SAE form.

Medication errors are reportable irrespective of the presence of an associated AE/SAE, including:

- Medication errors involving patient exposure to the product;
- Potential medication errors or uses outside of what is foreseen in the protocol that do or do not involve the participating patient.

Whether or not the medication error is accompanied by an AE, as determined by the Investigator, the medication error and, if applicable, any associated adverse event(s) is captured on an eCRF page (refer to Management, Timing and Assessment of Adverse Events section for further details).

Please refer to section 11.1 for specific management of overdoses.

5.5. General Concomitant Medication and Supportive Care Guidelines

Patients must be instructed not to take any additional medication (over-the-counter or other products) during the study without prior consultation with the Investigator. The use of any natural/herbal products or other "folk remedies" should be discouraged but use of these products, as well as use of all vitamins, nutritional supplements and all other concomitant medications from 28 days prior to the start of study treatment and up to approximately 30 days following the last dose of investigational product and the reason for their administration must be recorded in the eCRF.

Routine postoperative care, such as dressing changes, suture removal, drain removal, or venous access (central or peripheral), does not need to be recorded. Anaesthetics used for any surgical procedures performed during the patient's participation in the study can be recorded as "unspecified anaesthesia" on the concomitant treatment records; it is not necessary to list the specific anaesthetics. Palliative and supportive care for cancer-related symptoms will be offered to all patients in this study.

5.5.1. Medications that may NOT be administered

No other anti-cancer therapy (chemotherapy, immunotherapy, hormonal therapy (Hormone Replacement Therapy (HRT) is acceptable), radiotherapy, biological therapy or other novel agent) is to be permitted while the patient is receiving study medication.

Live virus and live bacterial vaccines should not be administered whilst the patient is receiving study medication and during the 30 day follow up period. An increased risk of infection by the administration of live virus and bacterial vaccines has been observed with conventional chemotherapy drugs and the effects with olaparib are unknown.

5.5.2. Restricted concomitant medications

5.5.2.1. Strong or Moderate CYP3A inhibitors

Known strong CYP3A inhibitors or moderate CYP3A inhibitors should not be taken with olaparib. While there is not an exhaustive list of CYP3A inhibitors the table below covers known CYP3A inhibitors.

Table 10. CYP3A inhibitors

CYP Enzymes	Strong Inhibitors ≥ 5-fold increase in AUC or > 80% decrease in Clearance (CL)	Moderate inhibitors ≥ 2 but < 5-fold increase in AUC or 50-80% decrease in CL	Weak inhibitors ≥ 1.25 but < 2-fold increase in AUC or 20-50% decrease in CL
CYP3A	Boceprevir, clarithromycin, conivaptan, grapefruit juice, indinavir, itraconazole, ketoconazole, lopinavir/ritonavir, mibepradil, nefazodone, nelfinavir, posaconazole, ritonavir, saquinavir, telaprevir, telithromycin, voriconazole, boosted protease inhibitors	Amprenavir, aprepitant, atazanavir, ciprofloxacin, darunavir/ritonavir, diltiazem, erythromycin, fluconazole, fosamprenavir, grapefruit juice imatinib, verapamil	Alprazolam, amiodarone, amlodipine, atorvastatin, bicalutamide, cilostazol, cimetidine, cyclosporine, fluoxetine, fluvoxamine, ginkgo, goldenseal, isoniazid, nilotinib, oral contraceptives, ranitidine, ranolazine, tipranavir/ritonavir, zileuton

If there is no suitable alternative concomitant medication then the dose of olaparib should be reduced for the period of concomitant administration. The dose reduction of olaparib should be recorded in the CRF with the reason documented as concomitant CYP3A inhibitor use; the reductions should be made as follows:

- Strong CYP3A inhibitors – reduce the dose of olaparib to 100 mg b.i.d. for the duration of concomitant therapy with the strong inhibitor and for 5 half-lives afterwards.
- Moderate CYP3A inhibitors - reduce the dose of olaparib to 150 mg b.i.d for the duration of concomitant therapy with the moderate inhibitor and for 3 half-lives afterwards.
- After the washout of the inhibitor is complete, the olaparib dose can be re-escalated.

In case of doubt about the procedure for concomitant administration of CYP3A inhibitors, the investigator should contact with GEICAM study team in order to avoid protocol deviations.

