1.4.3.4. Effect of Extrinsic Factors on the PK of Olaparib

The effect of food on olaparib tablet has been investigated. Study D0816C00004 has formally evaluated the effect of food (a high fat meal) on the PK of olaparib following dosing of the tablet formulation to man. The point estimates for the treatment ratio for AUC and AUC from time zero to the last measurable concentration (AUC_{0-t}) indicated a small (8%) increase in olaparib exposure when administered following a high fat meal which was of borderline statistical significance (treatment ratio: 1.08; 90% CI: 1.01-1.16). However, both the point estimate and 90% CI for the treatment ratios for AUC lay entirely within the 0.80 to 1.25 bounds, indicating that there was no effect of food on olaparib AUC. In contrast, there was a statistically significant 21% decrease in C_{max} following a high fat meal (treatment ratio: 0.79; 90% CI: 0.72-0.86). Co-administration with food slowed the rate of absorption (t_{max} delayed by 2.5 hours and C_{max} reduced by 21%), however food did not significantly affect the extent of absorption (AUC), therefore olaparib tablet can be given without regard to food.

Regarding drug-drug interactions:

- CYP3A4/5 are the isozymes predominantly responsible for the metabolic clearance of olaparib. All clinical studies conducted to date have excluded co-administration of known strong inhibitors or inducers of CYP3A4/5. The data in Study D0816C00007 indicated the presence of a marked interaction with a known strong inhibitor of CYP3A and P-glycoprotein (P-gp), itraconazole while the study D0816C00008 indicated the presence of marked interaction with a known strong inducer of CYP3A and Pgp, rifampicin. It is therefore recommended that known strong inhibitors or inducers of CYP3A4/5 isozymes should be avoided with olaparib.

Physiologically-based pharmacokinetic (PBPK) modeling has shown that moderate inhibitors will alter the clearance of olaparib and therefore concomitant use of moderate CYP3A inhibitors is not recommended with olaparib. It is also not recommended to consume grapefruit juice while on olaparib therapy.

If a strong or moderate CYP3A inhibitor must be co-administered, the recommended olaparib dose reduction is to 100 mg b.i.d. (equivalent to a total daily dose of 200 mg) with a strong CYP3A inhibitor or 150 mg b.i.d. (equivalent to a total daily dose of 300 mg) with a moderate CYP3A inhibitor.

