5.4. Special Treatment Considerations. Dose Adjustments of Olaparib

All dose modifications should be based on the worst preceding toxicity.

Every effort should be made to administer study treatment at the planned dose and schedule. However, in the event of significant treatment-related toxicity, administration of olaparib may need to be adjusted as described in the following sections. Depending on the nature of the toxicity observed, dose adjustments may be required for olaparib.

In the event of significant treatment-related toxicity, olaparib dosing may be interrupted and/or reduced. Patients are to be instructed to notify Investigators at the first occurrence of any adverse sign or symptom.

All dose modifications/adjustments must be clearly documented in the patient's source notes and the appropriate section of the eCRF.

Any toxicity observed during the course of the study could be managed by interruption of the dose of study treatment or dose reductions. Repeat dose interruptions are allowed as required, for a maximum of 4 weeks on each occasion. If the interruption is any longer, the GEICAM study team must be informed. Olaparib can be dose reduced to 250 mg twice daily as a first step and to 200 mg twice daily as a second step. If the reduced dose of 200 mg twice daily is not tolerable, no further dose reduction is allowed and study treatment should be discontinued.

Once dose is reduced, escalation is not permitted.

Olaparib recommended dose modifications for treatment related toxicities requiring treatment interruption/reduction or persisting despite optimal medical treatment are described in the following sections.

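### The fixed 150 mg b.i.d. olaparib dose with a moderate CYP3A inhibitor is not scaled for a patient already on 200 mg b.i.d.; at an assumed 2-fold AUC rise her exposure becomes about 1.5 times its previous level

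*Protocol*

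**What the plan says.** Protocol section 5.5.2.1 says that strong and moderate CYP3A inhibitors should not be taken with olaparib. If there is no suitable alternative, "the dose of olaparib should be reduced for the period of concomitant administration". For a moderate inhibitor the site is to "reduce the dose of olaparib to 150 mg b.i.d for the duration of concomitant therapy with the moderate inhibitor", and for three half-lives afterwards. Section 1.4.3.4 gives the same 150 mg b.i.d. Neither place refers to the dose the patient is on when the inhibitor starts.

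Other sections create lower dose levels. Section 5.4 states: "Olaparib can be dose reduced to 250 mg twice daily as a first step and to 200 mg twice daily as a second step". Table 9 repeats those steps. Section 5.4.2.3 recommends 200 mg b.i.d. when creatinine clearance falls to 31-50 mL/min. No section links these levels to the inhibitor dose.

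On the size of the interaction, section 1.4.3.4 reports only that modelling shows "moderate inhibitors will alter the clearance of olaparib". Table 10 defines its moderate class by "≥ 2 but < 5-fold increase in AUC".

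**The concern.** The rule is a definite dose that fits a patient on 300 mg b.i.d. A site that follows it exactly for a patient on 200 mg b.i.d. lowers the nominal dose by a quarter while clearance may fall by half or more. Her exposure can then rise, although her dose was lowered because she did not tolerate more or because her kidneys clear less drug.

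The haemoglobin findings make this more than bookkeeping. Section 1.4.5.3 reports a demonstrated exposure-response for falls in haemoglobin and names anaemia as the most common adverse reaction of grade 3 or higher. Under section 5.4, a patient who cannot tolerate 200 mg b.i.d. has no further toxicity step and stops treatment. What is at stake is avoidable toxicity, or loss of treatment, in a very small number of patients.

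**Working it through.** **Inputs**
- Starting dose 300 mg b.i.d. (section 5.1); second reduction step and renal dose 200 mg b.i.d. (sections 5.4 and 5.4.2.3).
- Dose with a moderate inhibitor 150 mg b.i.d. (section 5.5.2.1).
- AUC approximately proportional to dose (section 1.4.3.1).
- AUC rise f with a moderate inhibitor: not given for olaparib. The central assumption is f = 2, which is both the ratio 300/150 and the lower bound of Table 10's moderate class.
- Renal benchmarks from section 1.4.3.3: a 24% AUC rise (mild impairment) needs no dose change; for a 44% rise (moderate impairment) an adjustment is recommended.

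**Formula.** Exposure relative to before = inhibitor dose x f / previous dose.

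**Plan's own figure.** From 300 mg b.i.d.: 150 x 2 / 300 = 1.0. The written dose exactly offsets a 2-fold rise for a patient on the full dose.

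**Patient on 200 mg b.i.d.**

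| AUC rise f | Plan, 150 mg: 150f/200 | With 100 mg: 100f/200 |
|---|---|---|
| 1.25 | 0.94 | 0.63 |
| 1.33 | 1.00 | 0.67 |
| 1.5 | 1.13 | 0.75 |
| 2 | 1.50 | 1.00 |
| 2.5 | 1.88 | 1.25 |

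- Break-even for the plan's dose: 200/150 = 1.33-fold.
- At f = 2 the absolute level is 150 x 2 = 300 mg-equivalent, so she returns to about the exposure of 300 mg b.i.d. alone.
- A 50% rise exceeds the 44% for which the protocol itself recommends adjustment. The plan's dose reaches that benchmark when f = 1.44 x 200/150 = 1.92.

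**Moderate renal impairment.** Assume the 44% renal effect and the inhibitor effect multiply.
- 200 mg b.i.d., no inhibitor: 200 x 1.44 / 300 = 0.96 of the exposure at 300 mg b.i.d. with normal renal function.
- 150 mg b.i.d. with inhibitor: 150 x 1.44 x 2 / 300 = 1.44. Section 11.1 gives 300 mg b.i.d. as the maximum tolerated dose.
- 100 mg b.i.d. with inhibitor: 100 x 1.44 x 2 / 300 = 0.96, the level before the inhibitor.

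**How many patients.** The reduction rate documented in section 1.4.5.3 is 5.0%, for anaemia: 34 x 0.05 = 1.7 patients. If 5-20% of them need an inhibitor (assumption): 1.7 x 0.05 = 0.09 to 1.7 x 0.20 = 0.34. If 25% are reduced for any cause (assumption): 34 x 0.25 = 8.5, giving 8.5 x 0.05 = 0.43 to 8.5 x 0.20 = 1.7. These count every reduced patient; those at 200 mg b.i.d. are a subset.

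**The case against.** The strongest objection is that the harm rests on a number the documents do not contain. Table 10 sorts inhibitors into classes and does not say that its cut-offs are olaparib ratios. The strong-inhibitor dose does not match it either: 300 to 100 mg implies 3-fold, while the strong class starts at 5-fold. This stands. It is why 2-fold is labelled an assumption and the break-even is shown.

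Second, at 2-fold a patient reduced for toxicity goes back only to about starting-dose exposure, and only for a time. Between-patient variability in AUC is large (58.9% CV, section 1.4.3.1), and section 1.4.3.4 refers to a lack of relationship between exposure and safety. That remark supports combining olaparib with anti-hormonal agents, where tamoxifen lowered olaparib exposure; the haemoglobin finding in section 1.4.5.3 is specific and points the other way. The evidence on consequence is mixed.

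Third, there are safeguards. Inhibitors are excluded at entry and allowed only without an alternative, blood counts are taken each cycle, section 5.4.2.3 gives discretion over the renal dose, and doubtful cases go to the sponsor's study team. These make the case rare and limit its length. They do not correct the dose: a definite written instruction raises no doubt, the renal discretion does not mention the inhibitor dose, and section 5.5.2.2 asks for monitoring of efficacy, not toxicity, when an inhibitor is used.

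Three wider readings are tempting, and the documents do not support them.
- A reader might infer the same defect at 250 mg b.i.d. There the 2-fold ratio is 150 x 2 / 250 = 1.2, below the 24% rise that section 1.4.3.3 accepts without adjustment, and the break-even is 1.67-fold. Halving gives 125 mg, which cannot be made from 100 and 150 mg tablets; 100 mg would leave 0.8 of prior exposure at 2-fold and 0.6 at 1.5-fold.
- A reader might infer a similar excess with strong inhibitors, for which "the recommended olaparib dose reduction is to 100 mg b.i.d". From 200 mg b.i.d. the break-even is 2.0-fold, but the documents give no figure for the rise, so neither an excess nor a better dose can be derived.
- A reader might see a contradiction between "Once dose is reduced, escalation is not permitted" in section 5.4 and "After the washout of the inhibitor is complete, the olaparib dose can be re-escalated" in section 5.5.2.1. The first sits among the toxicity rules, and the inhibitor reduction is limited to the period of co-administration, so the natural meaning is a return to the previous dose.

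**Conclusion.** The gap is real for one group: patients already on 200 mg b.i.d. who need a moderate CYP3A inhibitor. Followed exactly, the plan gives them about 1.5 times their previous exposure. In moderate renal impairment this is about 1.44 times that of 300 mg b.i.d. with normal renal function. Both figures assume a 2-fold AUC rise and dose-proportional AUC; the second also assumes that the renal and inhibitor effects multiply. Below a 1.33-fold rise there is no excess.

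The weight is small: an optional improvement (COULD) that probably concerns fewer than one or two of 34 patients. A reader might infer from Table 10's upper bound that exposure could approach 150 x 5 / 200 = 3.75 times its previous level. The documents do not support that, because the table describes inhibitor classes and not measured effects on olaparib. Nor is there any effect on ORR, the two-stage decision rule or the error rates.

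**What to change.** Add one sentence to section 5.5.2.1: *A patient already taking 200 mg b.i.d. takes 100 mg b.i.d. with a moderate inhibitor and afterwards returns to 200 mg b.i.d.*

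This applies the protocol's own halving (300 to 150) to the 200 mg level, and 100 mg is a supplied tablet strength (section 5.2.1). It can go into the next amendment and needs no new visit, test or product. The price is lower exposure during the inhibitor course and its washout if the true AUC rise is below 2-fold, for example 100 x 1.5 / 200 = 0.75 of the previous level at 1.5-fold. No change is needed for the 250 mg level, strong inhibitors or section 5.4.

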5.5.2.2. Strong or Moderate CYP3A inducers

Strong and moderate CYP3A inducers of CYP3A should not be taken with olaparib. While there is not an exhaustive list, table 11 covers known CYP3A inducers.

Table 11. CYP3A inducers

CYP Enzymes	Strong Inducers ≥ 80% decrease in AUC	Moderate Inducers 50-80% decrease in AUC	Weak Inducers 20-50% decrease in AUC
CYP3A	Avasimibe, carbamazepine, phenytoin, rifampicin, St. John's wort, rifapentine, rifabutin, phenobarbital, nevirapine, enzalutamide.	Bosentan, efavirenz, etravirine, modafinil, nafcillin	Amprenavir, aprepitant, armodafinil, echinacea, pioglitazone, prednisone, rufinamide

If the use of any strong or moderate CYP3A inducers are considered necessary for the patient's safety and welfare this could diminish the clinical efficacy of olaparib.

If a patient requires use of a strong or moderate CYP3A inducer or inhibitor then they must be monitored carefully for any change in efficacy of olaparib.

5.5.3. P-gp inhibitors

It is possible that co-administration of P-gp inhibitors (e. g. amiodarone, azithromycin) may increase exposure to olaparib. Caution should therefore be observed.

5.5.4. Other Concomitant Medications

Based on limited *in vitro* data, olaparib may increase the exposure to substrates of CYP3A4, P-gp, OATP1B1, OCT1, OCT2, OAT3, MATE1 and MATE2K.

Based on limited *in vitro* data, olaparib may reduce the exposure to substrates of CYP3A4, CYP1A2, 2B6, 2C9, 2C19 and P-gp.

The efficacy of hormonal contraceptives may be reduced if co-administered with olaparib.

Caution should therefore be observed if substrates of these isoenzymes or transporter proteins are co-administered.

Examples of substrates include:

- CYP3A4 – hormonal contraceptive, simvastatin, cisapride, cyclosporine, ergot alkaloids, fentanyl, pimozide, sirolimus, tacrolimus and quetiapine
- CYP1A2 – duloxetine, melatonin

- CYP2B6 – bupropion, efavirenz
- CYP2C9 – warfarin
- CYP2C19 - lansoprazole, omeprazole, S-mephénytoïn
- P-gp - simvastatin, pravastatin, digoxin, dabigatran, colchicine
- OATP1B1 - bosentan, glibenclamide, repaglinide, statins and valsartan
- OCT1, MATE1, MATE2K – metformin
- OCT2 - serum creatinine
- OAT3 -furosemide, methotrexate

Any medications, with the exceptions noted in Section 5.5., which are considered necessary for the patient's welfare, and which it is believed will not interfere with the study medication, may be given at the discretion of the Investigator, providing the medications, the doses, dates and reasons for administration are recorded in the eCRF.

Standard therapies for pre-existing medical conditions, medical and/or surgical complications, and palliation. Any medication intended solely for supportive care (e.g., analgesics, anti-diarrhoeals, antidepressants) may also be used at the Investigator's discretion. All medications should be recorded in the eCRF.

In addition, any unplanned diagnostic, therapeutic or surgical procedure performed during the study period must be recorded in the eCRF.

The reason(s) for the use, doses and dates of treatment should be recorded in the patient's medical records and appropriate section of the eCRF.

Anticoagulant Therapy

Patients who are taking warfarin may participate in this trial; however, it is recommended that international normalised ratio (INR) be monitored carefully at least once per week for the first month, then monthly if the INR is stable. Subcutaneous heparin and low molecular weight heparin are permitted.

Anti-emetics/Anti-diarrhoeals

If a patient develops nausea, vomiting and / or diarrhoea, then these symptoms should be reported as AEs (see section 8.2.7. Safety Analyses) and appropriate treatment of the event given.

Palliative Radiotherapy

Palliative radiotherapy may be used for the treatment of pain at the site of bony metastases that were present at baseline, provided the Investigator does not feel that these are indicative of clinical disease progression during the study period. Study treatment should be discontinued for a minimum of 3 days before the patient undergoes therapeutic palliative radiation treatment. Study treatment should be restarted within 4 weeks as long as any bone marrow toxicity has recovered.

Administration of other Anti-cancer Agents

Patients must not receive any other concurrent anti-cancer therapy, including investigational agents, while on study treatment. Patients may continue the use of bisphosphonates or denosumab for bone disease and corticosteroids for the symptomatic control of brain metastases provided the dose is stable before and during the study and they were started at least 4 weeks prior to beginning study treatment.

Subsequent therapies for cancer

Details of first and subsequent therapies for cancer and/or details of surgery for the treatment of the cancer, after discontinuation of treatment, will be collected. Reasons for starting subsequent anti-cancer therapies including access to other PARP inhibitors or investigational drugs will be collected and could be included in the exploratory assessments of OS.

